8.4. Pharmacodynamic Assessments: Pharmacodynamic Biomarkers

Approximately 7 mL of blood will be collected for each sample. Pharmacodynamic biomarker samples will be sent to a central laboratory which will provide instructions and supplies to the study staff before study initiation.

Blood samples to measure cortisol (serum; $\mu g/dL$), 17-OHP (serum; ng/dL), androstenedione (serum; ng/dL), testosterone (serum; ng/dL), and ACTH (plasma; pg/mL) for Cohorts 1 and 2 will be collected at:

- Screening (for all biomarkers except 17-OHP; Section 8.2.1 describes sample collection for 17-OHP at screening).
- Day -7 to -6 (24-hour PD baseline): at approximately 2145, 2300, 2400, 0100, 0200, 0400, 0600, 0800, 1000, 1200, 1400, 1800, and 2200 hours.
- Days 1 and 14: 15 minutes predose and 1, 2, 3, 4, and 6 hours postdose (±5 minute window).
- Days 2 and 15: 8, 10, 12, 14, 16, 20, and 24 hours postdose (±15 minute window).
- Day 7: approximately 24 hours (-8 hour window) after the Day 6 dose and prior to the Day 7 dose.
- Days 21, 28, and 35: approximately 168 hours (-8 hours/+3 days), 336 hours (-8 hours/+3 days), and 504 hours (-8 hours/+3 days) postdose.
- Final study visit (Day 49 [+7 days] or early termination).

Blood samples to measure cortisol (serum; $\mu g/dL$), 17-OHP (serum; ng/dL), androstenedione (serum; ng/dL), testosterone (serum; ng/dL), and ACTH (plasma; pg/mL) for Cohorts 3 and 4

will be collected at (for Cohort 4, all times are relative to evening dosing unless otherwise noted):

- Screening (for all biomarkers except 17-OHP; Section 8.2.1 describes sample collection for 17-OHP at screening) (only for subjects who undergo screening).
- Day -7 to -6 (24-hour PD baseline): at approximately 1845, 2000, 2100, 2200, 2300, 2400, 0100, 0200, 0400, 0600, 0800, 1000, 1200, 1400, 1800, 1900, and 2200 hours.
- Day 7: 24 hours (-8 hour window) after the Day 6 dose and prior to the Day 7 dose for Cohort 3; 12 hours post morning dose but prior to the evening dose for Cohort 4 (-4 hour window).
- Day 14: 15 minutes predose and at 1, 2, 3, 4, and 5 hours postdose (±5 minute window).
- Day 15: 6, 7, 9, 11, 13, 15, 17, 19, 23, 24, and 27 hours postdose (±15 minute window).
- Days 21, 28, and 35: approximately 168 hours (-8 hours/+3 days), 336 hours (-8 hours/+3 days), and 504 hours (-8 hours/+3 days) postdose.
- Final study visit (Day 49 [+7 days] or early termination).

For the 24-hour serial blood draws, blood samples should be collected using an intravenous catheter inserted into a peripheral vein. Individual venipunctures can be used if there are complications with the intravenous catheter. Individual blood samples on other days should be collected by venipuncture.

Samples may be used for an exploratory assessment of changes in biomarkers associated with treatment with NBI-74788 (eg, metabolomics; these biomarkers do not include testing for specific genes). Data collected as part of this exploratory analysis will not be reported as part of the study results.

At any time during the study, an in-home service (phlebotomist) may be available for blood draws.

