8.2. Screening and Baseline Assessments

8.2.1. Serum 17-Hydroxyprogesterone

A a blood sample will be collected at screening (approximately 5 mL) to measure morning serum 17-OHP between 0700 and 1000 hours (prior to first morning dose of hydrocortisone) to determine subject eligibility. Subjects must have serum 17-OHP of \geq 1,000 ng/dL at screening to be eligible for study enrollment.

For Cohorts 3 and 4, subjects who are not required to undergo screening will not have this sample collected.

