9.3. Study Drug Administration

Cohorts 1 and 2

Subjects will take study drug capsule(s) by mouth at approximately 2200 hours for 14 consecutive days beginning on Day 1. Each dose of study drug is to be administered with a bottle of vanilla-flavored (~237 mL); subjects should finish consuming the entire bottle of within 30 minutes of taking study drug. The designated NBI-74788 dose (50 or 100 mg) will be administered as 1 or 2 NBI-74788 50 mg capsules.

Cohort 3

Subjects will take study drug capsules by mouth at approximately 1900 hours for 14 consecutive days beginning on Day 1. Each dose of study drug is to be administered with their evening meal; subjects should complete their evening meal within 30 minutes of taking study drug. The designated NBI-74788 dose (100 mg) will be administered as 2 NBI-74788 50 mg capsules.

Cohort 4

Subjects will take study drug capsules by mouth for 14 consecutive days beginning at approximately 1900 hours on Day 1; subsequently, study drug will be taken at approximately 0700 hours (with breakfast) and approximately 1900 hours (with evening meal). Subjects should complete their respective meals within 30 minutes of taking study drug. The designated NBI-74788 dose (100 mg) will be administered as 2 NBI-74788 50 mg capsules (200 mg total daily dose).

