12.7. Pharmacodynamic Data

The primary PD assessments are: morning 17-OHP (serum; ng/dL) from the 0600, 0800, and 1000 hour samples (8-, 10-, and 12-hour postdose samples from Cohorts 1 and 2 and 11-, 13-, and 15-hour postdose samples from Cohorts 3 and 4). Secondary PD assessments are: 17-OHP at all other times, androstenedione (serum; ng/dL), testosterone (serum; ng/dL), cortisol (serum; μ g/dL), and ACTH (plasma; pg/mL).

The PD assessments listed above will be summarized with descriptive statistics (including change from predose) and in graphical displays by dose cohort and timepoint.

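### Follow-up PD draws on Days 21, 28, 35 and 49 have no fixed clock time or steroid timing, yet Section 12.7 tabulates them as change from predose by nominal timepoint

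*Combined protocol and SAP*

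**What the plan says.** Section 12.7 ties the primary PD assessment to the clock: "morning 17-OHP (serum; ng/dL) from the 0600, 0800, and 1000 hour samples", which it equates to "8-, 10-, and 12-hour postdose samples from Cohorts 1 and 2 and 11-, 13-, and 15-hour postdose samples from Cohorts 3 and 4". It continues: "Secondary PD assessments are: 17-OHP at all other times". All PD assessments are to be "summarized with descriptive statistics (including change from predose) and in graphical displays by dose cohort and timepoint".

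Clock and steroid timing are set at screening and on the serial-sampling days. Section 8.2.1 takes a sample to "measure morning serum 17-OHP between 0700 and 1000 hours (prior to first morning dose of hydrocortisone"). The usual morning steroid waits until after the 1000 sample on Day -6 and on Day 2 (Cohorts 1 and 2), and until after the 1400 sample on Day 15. On the treatment days in between it is placed at about 1000 (Sections 8.7.3 and 8.8.3).

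The follow-up draws are set in elapsed time: "Days 21, 28, and 35: approximately 168 hours (-8 hours/+3 days), 336 hours (-8 hours/+3 days), and 504 hours (-8 hours/+3 days) postdose". Day 49 has a +7 day window and neither a clock time nor hours postdose. No section sets the hour of steroid intake after Day 15.

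**The concern.** The fixed morning window and the 24-hour baseline profile show that the plan regards time of day, and time relative to the steroid dose, as material to these hormones. The follow-up draws carry neither control, and Section 12.7 describes no time-matching.

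A change-from-predose row for Day 21, 28, 35 or 49 could therefore reflect three things at once: loss of drug effect after the last dose, the hour at which each subject was drawn, and how long before the draw the steroid was taken. With about 8 to 10 subjects per cohort (up to 8 in Cohort 4) and no control arm, a few draws at a different time of day could move a cohort mean. At stake is whether the four post-treatment PD samples per subject can be interpreted.

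**Working it through.** **1. The plan's own equivalence.** Cohorts 1 and 2 dose at 2200 (Section 9.3: "Subjects will take study drug capsule(s) by mouth at approximately 2200 hours for 14 consecutive days beginning on Day 1"); the evening dose in Cohorts 3 and 4 is at 1900.
- 2200 + 8, 10, 12 h = 0600, 0800, 1000.
- 1900 + 11, 13, 15 h = 0600, 0800, 1000.

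Section 12.7 is reproduced.

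**2. Follow-up windows.** Window = Day 14 dose time + nominal hours, from -8 h to +72 h. Length = 8 + 72 = 80 h.

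| Day 21 visit | Nominal | Opens | Closes |
|---|---|---|---|
| Cohorts 1-2 | Day 21, 2200 | Day 21, 1400 | Day 24, 2200 |
| Cohorts 3-4 | Day 21, 1900 | Day 21, 1100 | Day 24, 1900 |

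Days 28 and 35 repeat this pattern 7 and 14 days later. Since 80 h exceeds three full days, every clock hour is allowed.

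**3. Share in the primary morning interval.** 0600 to 1000 falls inside the window on three mornings (Days 22, 23 and 24): 3 × 4 = 12 h, and 12/80 = 15%. Overlap on Day 21 itself is 0 h.

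If draws happen only in staffed hours (assumed; the documents give none), the range is:
- 0800-1800, Cohorts 1-2: 4 + 3 × 10 = 34 h, of which 3 × 2 = 6 h are morning; 17.6%.
- 0700-1900, Cohorts 1-2: 5 + 3 × 12 = 41 h, of which 3 × 3 = 9 h; 22.0%.
- 0800-2000, Cohorts 3-4: 9 + 12 + 12 + 11 = 44 h, of which 6 h; 13.6%.

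**4. The predose reference.** In Cohorts 1 and 2 the sample before the first dose is at about 2145 on Day 1. Table 3 has no Day 1 PD sample for Cohorts 3 and 4. The candidates there are the 1845 sample on Day -7 and the Day 14 predose sample, which follows 13 days of dosing. Section 12.7 does not say which is meant.

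**5. What could be recovered afterwards.** Section 8.3 records the exact sampling time for PK; Section 8.4 has no such sentence, but PK and PD share these visits. Section 8.10.1 asks for dates, not clock times, of concomitant drugs. The diary covers study drug only and is returned on Day 14. Clock-matching is therefore feasible, but matching on time since steroid is not assured.

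**6. Day 7.** Cohorts 1 and 2 are drawn "approximately 24 hours (-8 hour window) after the Day 6 dose and prior to the Day 7 dose".
- Cohorts 1-2: 2200 + 16 to 24 h = 1400-2200.
- Cohort 3: 1900 + 16 to 24 h = 1100-1900.
- Cohort 4: 0700 + 8 to 12 h = 1500-1900.

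All open after the steroid at about 1000, the same order as on Day -6. Baseline samples exist at 1400, 1800 and 2200 (Cohorts 1-2) and at 1200, 1400, 1800 and 1900 (Cohorts 3-4). In Cohorts 1-2 the Day 2 samples at 16, 20 and 24 h also fall at 1400, 1800 and 2200.

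**7. Does a morning draw fit the present window?** The 168 h visit allows 168 - 8 = 160 h to 168 + 72 = 240 h.
- Day 14, 2200 to Day 22, 0700-1000 = 177-180 h.
- Day 14, 1900 to Day 22, 0700-1000 = 180-183 h.

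Both fit. The shift from nominal is 177 - 168 = 9 h to 183 - 168 = 15 h, and is the same at 336 h and 504 h.

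**The case against.** The nominal times have a logic. 168, 336 and 504 h after the last dose fall at about 2200 or 1900, within about 15 minutes of the clock time of a 2145 or 1845 predose sample, so a draw on schedule is nearly clock-matched. That stands, but only at the nominal time. The window allows any hour, and 2200 lies outside all three staffed-hour ranges assumed above.

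The steroid regimen must also stay stable throughout. That fixes the regimen, not the hour of intake.

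It is also fair that 17-OHP outside the morning samples is declared secondary, that everything is descriptive, and that no objective names recovery or rebound after stopping. This is therefore a design limitation, not a contradiction in the plan.

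A reader might infer that Day 7 has the same fault, so that the marker cannot be followed during treatment or compared with Day 2. The documents do not support this. The morning measure is not scheduled on Day 7, but Day 7 is confined to 4 to 8 afternoon or evening hours after a steroid dose at about 1000. It can be read against baseline in every cohort, and against Day 2 in Cohorts 1 and 2.

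**Conclusion.** The point holds for Days 21, 28, 35 and 49. As written, their change-from-predose rows can mix time of day and time since steroid with drug washout. The size that can be stated is the 80-hour window, of which 15% lies in 0600-1000 (about 14% to 22% under the assumed staffed hours). Day 49 has no clock time at all.

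A reader might want to turn this into a percentage error in 17-OHP. That needs a within-day peak-to-trough ratio, which the documents do not give, so none is offered. Nor does the point reach the primary morning measure: on Days -6, 2 and 15 its clock times are fixed and the steroid dose follows the 1000 sample.

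The conclusion assumes that predose keeps its ordinary meaning of a single pre-treatment value and that no time-matching is planned beyond what Section 12.7 states. It is a cheap improvement to data the study already collects.

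**What to change.** - **Tables 2 and 3 and Section 8.4:** set one common clock window for the Day 21, 28, 35 and 49 PD draws. 0700-1000 on the morning after the nominal day fits the present window for the first three. It matches the clock window of the screening draw and the Day -6 samples at 0800 and 1000. Day 49 needs only the clock window added.
- **Section 8.4 and the eCRF:** record the PD draw time and the clock time of the last steroid dose before each draw.
- **Section 12.7:** compute change for Days 7, 21, 28, 35 and 49 against the nearest clock-time sample of the Day -7/-6 baseline instead of a single predose value, with a rule for ties (0700 is equidistant from 0600 and 0800). The largest gap in either baseline grid is 4 h, so the nearest sample is never more than about 2 h away.

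Whether steroid intake is held before follow-up draws is for the sponsor to reconcile with the screening and Day -6 passages. No steroid rule is proposed here.

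The cost is morning scheduling of home or site visits, two recorded times, and a paired PK sample that moves 9 to 15 h within its existing window. No visit or blood volume is added.

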8.5. Safety Assessments

Concomitant medication use and AEs will be monitored throughout the study as described in Section 8.10.1 and Section 10, respectively. Additional safety assessments are described in the following sections.

Appropriate psychiatric evaluation and intervention will be provided for any treatment-emergent suicidal behavior or clinically significant suicidal ideation.

For any abnormal safety assessment deemed clinically significant, the investigator will perform appropriate follow-up assessments (eg, repeat analysis), until the cause of the abnormality is determined and/or until the value returns to baseline (or within normal limits), or the investigator deems the abnormality to be of no clinical significance.

8.5.1. Vital Sign Measurements

Vital sign measurements, including orthostatic systolic and diastolic blood pressures, orthostatic heart rate, respiratory rate, and oral body temperature will be conducted. Blood pressure will be

measured using a calibrated automatic blood pressure cuff after the subject has been supine for at least 5 minutes and after approximately 2 minutes of standing. The automatic blood pressure cuff will also provide pulse rate measurement.

Vital sign measurements will be collected once per day (other than on Days 2 and 15, as indicated below) and will generally be obtained before scheduled blood sample collection. Vital sign measurements will be collected at the following times (for Cohort 4, all times are relative to evening dosing):

- Screening.
- Day -7 (PD baseline).
- Day 1.
- Days 2 and 15 (between 8-10 and 22-24 hours postdose [ie, morning and evening]) (Day 2 only applies to Cohorts 1 and 2).
- Day 7.
- Day 14.
- Day 49 (or early termination).

8.5.2. Medical History and Physical Examination

A medical history will be taken at the screening visit and updated on Day -7 and Day 1 (only for subjects who undergo screening).

A complete physical examination including weight will be conducted at screening, on Day 1, Day 2 (Cohorts 1 and 2 only), Day 7, Day 15, and Day 49 (or final study visit for subjects who terminate early). The complete physical examination will consist of an assessment of general appearance, skin and mucosae, head, eyes, ears, nose, throat, neck (including thyroid), lymph nodes, chest/lungs, cardiovascular, abdomen, extremities, neurological and musculoskeletal systems. Height and weight will be measured with subjects not wearing shoes. Height will be measured only at screening. Weight will be measured at screening, on Day 1, Day 15, and Day 49 (or final study visit for subjects who terminate early).

8.5.3. 12-Lead Electrocardiogram

12-lead ECG will be conducted in triplicate (1-3 minutes apart) after the subject has rested supine for at least 5 minutes at the following times (for Cohort 4, all times are relative to evening dosing):

- Screening.
- Days 1 and 14 (predose).
- Days 2 and 15: prior to visit completion or discharge (Day 2 only applies to Cohorts 1 and 2).
- Day 49 (or final study visit for subjects who terminate early).

The ECG parameters that will be assessed include heart rate, PR interval, QRS duration, QT interval, and QTcF (machine readings). Additionally, the occurrence of de- and re-polarization and rhythm disorders or other abnormalities will be assessed. Based on the review of these
parameters, the investigator or designee will note if the ECG is Normal, Abnormal Not Clinically Significant, or Abnormal Clinically Significant. If the ECG is Abnormal Clinically Significant, the investigator will provide a description of the abnormality recorded on the AE eCRF.

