Eligible subjects who have a screening 17-OHP level \geq 1,000 ng/dL will be admitted to the study center for 1 night and have baseline serial PD samples collected over a 24-hour period beginning in the evening of Day -7. Baseline serial PD samples will be collected at approximately 2145, 2300, 2400, 0100, 0200, 0400, 0600, 0800, 1000, 1200, 1400, 1800, and 2200 hours for Cohorts 1 and 2 and at approximately 1845, 2000, 2100, 2200, 2300, 2400, 0100, 0200, 0400, 0600, 0800, 1000, 1200, 1400, 1800, and 2200 hours for Cohorts 3 and 4. The subjects' usual morning dose of steroidal treatments will be administered after the 1000 hours PD sample is collected on Day -6. Subjects will be discharged on Day -6 after the last PD sample is collected.

Subjects in Cohorts 1 and 2 will be admitted to the study center on Days 1 and 14 (first and last day of dosing). Subjects will have a blood sample collected on Day 1 for

Baseline safety assessments will be collected on Day 1 prior to the first dose of study drug. Study drug (NBI-74788 50 or 100 mg) will be administered at approximately 2200 hours. The subjects' usual morning dose of concurrent steroidal treatments will be administered after the 12-hour postdose PK/PD samples are collected (ie, at approximately 1000 hours) on Day 2 and after the 16-hour postdose PK/PD samples are collected (ie, at approximately 1400 hours) on Day 15. Subjects will be discharged from the study center the evening on Days 2 and 15 following completion of all study-related procedures for those days. Prior to this discharge on Day 2, study drug will be administered at the study center at approximately 2200 hours. Study drug will then be self-administered nightly at home at approximately 2200 hours on Days 3 to 13. Subjects will take their usual morning dose of concurrent steroidal treatments at approximately 1000 hours on Days 3 to 14. On Day 7 during the treatment period, PK, PD, and safety assessments will be conducted in an outpatient setting at the study center.

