- ^a Final study visit for subjects who complete the study (or early termination). The final study visit will be conducted approximately 5 weeks (+7 days) after the last dose of study drug.
- ^b Day 1 occurs 1 week after the Day -7 visit. Day 1 assessments will be collected predose unless otherwise noted below. Safety assessments collected predose on Day 1 will serve as the baseline.
- ^c Vital signs will be collected on Days 2 and 15 between 8-10 and 22-24 hours postdose (ie, morning and evening).
- ^d A standard 12-lead ECG will be conducted in triplicate (1-3 minutes apart) after subject has rested supine for at least 5 minutes at screening, at pre-evening dose on Days 1 and 14, prior to visit completion or discharge on Days 2 and 15, and at the final study visit (Day 49 or early termination).
- ^e Pregnancy tests will be conducted for female subjects of childbearing potential. Serum pregnancy tests will be conducted at screening and urine pregnancy tests will be conducted on Day -7, prior to dosing on Day 1 (for eligibility), Day 14, and at the final study visit (Day 49 or early termination).
- ^f Blood sample for determination of study-qualifying levels of 17-OHP should be collected between 0700 and 1000 hours (prior to first morning dose of hydrocortisone).
- ^g Includes hematology, clinical chemistry (including creatine kinase, myoglobin, total and conjugated bilirubin), coagulation (prothrombin time, activated partial thromboplastin time [aPTT], d-dimer, fibrinogen), and urinalysis (including quantitative myoglobin, casts and crystals). Samples will be obtained under nonfasted conditions.
- ^h Urine testing kits will be provided by the central laboratory to confirm negative drug screen prior to Day -7 PD collection and Day 1 dosing. Separate urine sample will also be sent to the central laboratory for analysis.
- ⁱ Blood samples for analyses of 17-OHP, androstenedione, testosterone, cortisol, and adrenocorticotropic hormone [ACTH] will be collected at the following times:
- Screening (for all biomarkers except 17-OHP).
- Day -7 to Day -6 (24-hour PD baseline): at approximately 2145, 2300, 2400, 0100, 0200, 0400, 0600, 0800, 1000, 1200, 1400, 1800, and 2200 hours.
- Days 1 and 14: 15 minutes predose and at 1, 2, 3, 4, and 6 hours postdose (±5 minute window).
- Days 2 and 15: 8, 10, 12, 14, 16, 20, and 24 hours postdose (±15 minute window).
- Day 7: approximately 24 hours (-8 hour window) after the Day 6 dose and prior to the Day 7 dose.

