- ^g A standard 12-lead ECG will be conducted in triplicate (1-3 minutes apart) after subject has rested supine for at least 5 minutes at screening, at pre-evening dose on Days 1 and 14, prior to visit completion or discharge on Day 15, and at the final study visit (Day 49 or early termination).
- ^h Pregnancy tests will be conducted for female subjects of childbearing potential. For subjects who undergo screening, serum pregnancy tests will be conducted at screening and urine pregnancy tests will be conducted on Day -7, prior to dosing on Day 1 (for eligibility), Day 14, and at the final study visit (Day 49 or early termination). For subjects who do not undergo screening, serum pregnancy tests will be conducted on Day -7 and urine pregnancy tests will be conducted prior to dosing on Day 1 (for eligibility), Day 14, and at the final study visit (Day 49 or early termination).
- ⁱ Only for subjects who have not previously enrolled in Cohorts 1 or 2.
- ^j Blood sample for determination of study-qualifying levels of 17-OHP should be collected between 0700 and 1000 hours (prior to first morning dose of hydrocortisone).
- ^k Includes hematology, clinical chemistry (including creatine kinase, myoglobin, total and conjugated bilirubin), coagulation (prothrombin time, activated partial thromboplastin time [aPTT], d-dimer, fibrinogen), and urinalysis (including quantitative myoglobin, casts and crystals). Samples will be obtained under nonfasted conditions.
- ¹ Urine testing kits will be provided by the central laboratory to confirm negative drug screen prior to Day -7 PD collection and Day 1 dosing. Separate urine sample will also be sent to the central laboratory for analysis.
- ^m Blood samples for analyses of 17-OHP, androstenedione, testosterone, cortisol, and adrenocorticotropic hormone [ACTH] will be collected at the following times:
- Screening (for all biomarkers except 17-OHP).
- Day -7 to Day -6 (24-hour PD baseline): at approximately 1845, 2000, 2100, 2200, 2300, 2400, 0100, 0200, 0400, 0600, 0800, 1000, 1200, 1400, 1800, 1900, and 2200 hours.
- Day 7: 24 hours (-8 hour window) after the Day 6 dose and prior to the Day 7 dose (Cohort 3); 12 hours post morning dose but prior to the evening dose for Cohort 4 (-4 hour window).
- Day 14 (for Cohort 4, all times are relative to the evening dose): 15 minutes predose and at 1, 2, 3, 4, and 5 hours postdose (±5 minute window).

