8.3. Pharmacokinetic Assessments

For the 24-hour serial blood draws, blood samples should be collected using an intravenous catheter inserted into a peripheral vein. If a catheter becomes unusable, either a new catheter may be inserted, or the remaining samples may be collected by venipuncture. Individual blood samples on other days should be collected by venipuncture. The catheter will be inserted in the evening and removed before the subject is discharged from the study center the following evening.

For postdose blood sample collection performed while subjects are asleep, every effort should be made to minimize disturbances to the subjects.

PK plasma samples for analyses of NBI-74788 will be collected at the following times for Cohorts 1 and 2:

- Days 1 and 14: 15 minutes predose and at 1, 2, 3, 4, and 6 hours postdose (±5 minute window).
- Days 2 and 15: 8, 10, 12, 14, 16, 20, and 24 hours postdose (±15 minute window).
- Day 7: approximately 24 hours (-8 hour window) after the Day 6 dose and prior to the Day 7 dose.
- Days 21, 28, and 35: approximately 168 hours (-8 hours/+3 days), 336 hours (-8 hours/+3 days), and 504 hours (-8 hours/+3 days) postdose.
- Final study visit (Day 49 [+7 days] or early termination).

PK plasma samples for analyses of NBI-74788 will be collected at the following times for Cohorts 3 and 4 (for Cohort 4, all times are relative to evening dosing unless otherwise noted):

- Day 7: 24 hours (-8 hour window) after the Day 6 dose and prior to the Day 7 dose for Cohort 3; 12 hours post morning dose but prior to the evening dose for Cohort 4 (-4 hour window).
- Day 14: 15 minutes predose and at 1, 2, 3, 4, and 5 hours postdose (±5 minute window).
- Day 15: 6, 7, 9, 11, 13, 15, 17, 19, 23, 24, and 27 hours postdose (±15 minute window).
- Days 21, 28, and 35: approximately 168 hours (-8 hours/+3 days), 336 hours (-8 hours/+3 days), and 504 hours (-8 hours/+3 days) postdose.
- Final study visit (Day 49 [+7 days] or early termination).

A PK sample should be collected from subjects who terminate early. The exact time of sampling in hour and minutes will be recorded.

The blood samples will be processed to plasma, which will be stored as specified in the laboratory manual. These samples will be shipped on dry ice to the central laboratory for analysis. Refer to the laboratory manual for additional details.

Plasma samples remaining at the end of the study may be used for exploratory assessments of NBI-74788 metabolites.

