8.11. Withdrawal Criteria

8.11.1. Reasons for Withdrawal

Subjects are free to discontinue their participation in the study at any time. The investigator must withdraw any subject from the study if that subject requests to be withdrawn.

The investigator must withdraw the subject from the study if the subject experiences any of the following:

- If the type, frequency, or severity of any AE becomes unacceptable/intolerable.
- QTcF value >500 msec (one or more value; cardiologist verified).
- Is lost to follow up.
- Subject is confirmed to be pregnant.

The investigator or NBI may withdraw the subject from the study for other reasons as described below. These should be discussed on a case-by-case basis with the NBI medical monitor (or designee) prior to withdrawing the subject from the study.

- Develops an ECG abnormality.
- Liver function test values for AST or ALT exceed 2.5 times ULN, GGT exceeds 3 times ULN, or total bilirubin exceeds 2 times ULN.
- Creatinine value exceeds 1.5 times ULN.

- Positive urine drug or alcohol screen.
- Requires a medication that is prohibited by the protocol (refer to Section 8.10.1).

All subjects prematurely discontinuing the study, regardless of cause, should have all early termination assessments performed (see Section 8.7.4.2).

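### No scheduled ECG is tied to the early postdose PK draws and the Day 2/15 ECG has no stated hour, so the ECG tables describe mainly trough or late-interval readings

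*Combined protocol and SAP*

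**What the plan says.** Section 8.5.3 lists triplicate ECGs at screening, "Days 1 and 14 (predose"), on Days 2 and 15 before the subject leaves, and at Day 49 or early termination. For Cohort 4 the times are relative to the evening dose. The end-of-stay item reads "Days 2 and 15: prior to visit completion or discharge (Day 2 only applies to Cohorts 1 and 2"). The table footnotes agree: "at pre-evening dose on Days 1 and 14, prior to visit completion or discharge on Days 2 and 15" for Cohorts 1 and 2 (Table 2, footnote d) and "at pre-evening dose on Days 1 and 14, prior to visit completion or discharge on Day 15" for Cohorts 3 and 4 (Table 3, footnote g). The visit sections (8.7.3 and 8.8.3) list no ECG among the procedures after dosing on Day 1 or Day 14. No cohort has an ECG on Day 7.

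Section 8.3 sets the PK draws. For Cohorts 1 and 2: "Days 1 and 14: 15 minutes predose and at 1, 2, 3, 4, and 6 hours postdose (±5 minute window"). For Cohorts 3 and 4: "Day 14: 15 minutes predose and at 1, 2, 3, 4, and 5 hours postdose (±5 minute window").

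Section 8.11.1 makes one finding a compulsory reason for withdrawal: "QTcF value >500 msec (one or more value; cardiologist verified"). An emergent ECG abnormality is a further, discretionary reason. Section 12.8 summarises ECG data descriptively by cohort and timepoint.

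**The concern.** Safety and tolerability is the first objective, and Cohort 4 receives the highest daily dose in the study (200 mg). If a QTc effect follows plasma concentration, it is largest near the peak. The plan samples blood closely in the hours where it expects to find Cmax and tmax, but reads no ECG there. QTcF therefore cannot be set against concentration in that window, and an unremarkable ECG table could be given more weight than its timing supports.

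The second issue is definition. Vital signs on Days 2 and 15 have stated postdose windows (8 to 10 h and 22 to 24 h, Section 8.5.1). The ECG on the same days has none, so one row of the ECG summary may pool readings taken many hours apart.

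The third is how the schedule fits the QTcF withdrawal criterion in Cohorts 3 and 4, where few doses remain when the first on-treatment ECG is read.

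**Working it through.** The plan gives no QTc detection figure or power calculation, so there is none to reproduce. The check rebuilds the dosing and ECG clock.

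**Inputs.** Dosing at about 2200 (Cohorts 1 and 2), 1900 (Cohort 3), and 0700 and 1900 (Cohort 4), from Sections 6.1 and 9.3. Waking at 0600 on Days 2 and 15 is stated for Cohorts 1 and 2 only (Sections 8.7.3 and 8.10.2). The last draw is at 24 h (Cohorts 1 and 2) or 27 h (Cohorts 3 and 4).

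**Number of doses**
- Cohorts 1, 2 and 3: 14 each.
- Cohort 4: 14 evening doses (Days 1 to 14) + 13 morning doses (Days 2 to 14) = 27.

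**On-treatment ECGs**

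| Cohort | ECG | Hours since last dose | Doses still to come |
|---|---|---|---|
| 1, 2 | Day 2 | 8 (0600) to 23.75 (2145) | 13, or 12 if taken after the Day 2 dose |
| 1, 2 | Day 14 predose | 23.75 if at 2145 | 1 |
| 1, 2 | Day 15 | 8 to 24 | 0 |
| 3 | Day 14 predose | 23.75 if at 1845 | 1 |
| 3 | Day 15 | 5 (midnight) to 27 | 0 |
| 4 | Day 14 pre-evening | 11.75 if at 1845; 5 if at noon | 1 |
| 4 | Day 15 | 5 (midnight) to 27 | 0 |

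The Day 2 ECG could even follow that evening's dose, because "Prior to this discharge on Day 2, study drug will be administered at the study center at approximately 2200 hours".

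Scheduled ECGs assigned to the early postdose draws: none in any cohort.

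Doses taken before the Day 14 ECG are 13 of 14 in Cohort 3 and 13 + 13 = 26 of 27 in Cohort 4. Neither cohort has a scheduled ECG between Day 1 predose and that reading.

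**How much a trough reading could miss.** This is a sensitivity check on assumed values. It uses a one-compartment oral model at steady state with absorption rate ka = 0.5 to 1.0 per hour and half-life 4 to 96 h. With ke = ln 2 / half-life and dosing interval τ,

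C(t) ∝ Σ over k of [exp(−ke(t + kτ)) − exp(−ka(t + kτ))], and trough/peak = C(τ) / max C(t).

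| Assumed half-life | Once daily (τ = 24 h) | Twice daily (τ = 12 h) |
|---|---|---|
| 4 h | 0.03–0.04 | 0.21–0.31 |
| 12 h | 0.31–0.36 | 0.61–0.68 |
| 24 h | 0.56–0.61 | 0.78–0.83 |
| 96 h | 0.87–0.88 | 0.94–0.95 |

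If the effect is proportional to concentration, an assumed 15 msec effect at peak would read at trough as 15 × 0.03 = 0.45 to 15 × 0.88 = 13.2 msec once daily, and 15 × 0.21 = 3.15 to 15 × 0.95 = 14.25 msec twice daily. The twice-daily ratios apply to the Cohort 4 Day 14 reading taken just before the evening dose. Its Day 15 reading may come up to 27 h after the last dose, beyond the 12 h interval, where concentrations are lower still.

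**The case against.** A reader might infer that the plan cannot detect a QTc effect at peak exposure. The documents do not support this. No tmax or half-life is public, Section 4.2 is withheld and Section 4.3 is partly withheld; earlier QTc data may sit there. PK sampling continues to 504 h and Day 49, so slow elimination cannot be excluded. With a long half-life, most of a concentration-related effect would still be visible at trough.

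A reader might also infer that no ECG can fall within the first 8 h after a dose, or the first 11 h in Cohorts 3 and 4. That treats open times as fixed. The 0600 waking is not stated for Cohorts 3 and 4, whose Day 15 begins 5 h postdose, and the Cohort 4 Day 14 ECG may come soon after the morning dose. What stands is that no ECG is assigned to the early window.

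Finally, a reader might infer that the withdrawal criterion has almost nothing to act on. That fails for Cohorts 1 and 2, where the Day 2 ECG precedes 12 or 13 of 14 doses. In all cohorts there is also follow-up of clinically significant findings (Section 8.5), the discretionary ECG criterion, and entry exclusions for QT. It is also fair to say that the study has no QTc-specific objective and that the ECG analysis is descriptive only.

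None of this supplies an ECG timed to the early draws or an hour for the end-of-stay reading.

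**Conclusion.** The concern holds in a limited form. Every on-treatment ECG is either predose or at an unstated hour before discharge, and none is tied to the early postdose PK draws. The ECG summaries will therefore describe mainly trough or late-interval readings. The end-of-stay row may pool about 8 to 24 h postdose in Cohorts 1 and 2, or about 5 to 27 h in Cohorts 3 and 4. These statements rest on the schedule alone.

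The size of any missed effect is open. It depends on tmax and half-life, and the assumed range runs from nearly all of the peak being missed to very little.

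For the QTcF withdrawal criterion, the mismatch is confined to Cohorts 3 and 4: one scheduled ECG before dosing ends, with one dose left. It does not apply in the same way to Cohorts 1 and 2. This is a worthwhile, inexpensive improvement to the schedule; it does not show that the safety assessment fails.

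**What to change.** **Cohorts 3 and 4.** In Section 8.5.3, Table 3 footnote g and the Day 14/15 visit section, take the existing end-of-stay triplicate on Day 14 with the postdose PK draw nearest the tmax the sponsor expects. One of the 2 to 4 h draws (2100 to 2300) is an example; subjects are already inpatients. Keep the Day 14 predose ECG as the trough reading, and list QTcF change beside the paired concentration.

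**Cohorts 1 and 2.** In Section 8.5.3 and Table 2 footnote d, state a fixed hour postdose for the Day 2 and Day 15 ECGs, paired with a PK draw. An 8 h reading, at waking, would be defined but would still leave the early window uncovered.

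**Cost.** The number of ECGs does not change. In Cohorts 3 and 4 the late Day 15 reading (24 to 27 h if taken near discharge) is lost. In Cohort 3 the Day 14 predose ECG already gives a trough at about 24 h. In Cohort 4 it gives only a trough at about 12 h, so the later reading is not replaced.

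**Withdrawal criterion.** The sponsor must reconcile Section 8.11.1 with the Cohort 3 and 4 ECG schedule. Retiming does not resolve this, because the moved ECG follows the last dose. The content of the criterion is for the sponsor.
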